## 6 STUDY EXPOSURE

### 6.1 STUDY EXPOSURE DEFINITION

For this target trial emulation, exposure is whether a thyroid ultrasound is performed within 3 months of the index PET-CT.

### 6.2 MEASURES TO MINIMIZE BIAS

Data extraction from the electronic health record data warehouse using SQL and Python scripts will necessarily be conducted with patient identifiers. All data will be anonymized prior to analysis and all blinded data utilized for analysis will be published publicly as utilized in the analysis. Study group assignments will be strictly performed based on whether or not thyroid ultrasound was performed within the 3-month period following the PET-CT; there is no subjectivity to the assignment.

### 6.3 LOST TO FOLLOW-UP

Complete mortality data is available in the electronic health record via regular updates from electronic death registry systems and from 5 state death registries, regardless of patients' continued care within the study healthcare system; so there is no loss to follow-up for the primary outcome. The 3-month grace period between the PET examination and the ultrasound will be addressed with clone-censor weighting. For the secondary outcomes, we will consider patients who did not have any provider note for 2-years following the PET-CT to be lost to follow-up.

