### 1.2 TARGET VS. EMULATED TRIAL TABLE

	Target Clinical Trial	Observational Emulation
Design	Non-inferiority randomized controlled trial	Retrospective non-inferiority cohort study
Aim	Assess whether all-cause mortality in patients with an incidental thyroid nodule on PET-CT who did	Same

	not have thyroid ultrasound within 3 months is no worse than 5% higher than those who did have ultrasound	
Inclusion	Thyroid nodule on PET-CT Age 18 or older Clinic note within 36-months before the PET-CT	Same, with PET-CT scans between 1/1/2015 to 12/31/2021
Exclusion	Prior PET reported thyroid nodule Thyroid ultrasound in prior 3 years Prior thyroid cancer diagnosis	Same
Treatment Strategies	(1) Thyroid ultrasound ordered to be performed within 3 months (2) No thyroid ultrasound ordered	(1) Thyroid ultrasound performed within 3 months (2) No thyroid ultrasound performed within 3 months
Treatment Assignment	Randomized to treatment strategy	Non-randomized to treatment strategy. Randomization emulated via cloning patients in both arms.
Treatment Implementation	3-month grace period	3-month grace period
Outcome	All-cause mortality	Same
Type of Outcome	Failure time	Same
Follow-up Start	PET-CT date, equivalent to treatment assignment	PET-CT date, not equivalent to treatment assignment
Follow-up End	Earliest of death, 7-years from follow-up start, or study end	Same
Censoring	Administrative censoring	Administrative censoring Artificial censoring of clones
Causal Contrast	Intention to treat and per protocol	Per protocol effect only
Non-Inferiority Margin	5%	Same
Statistical Analysis	Non-inferiority intention to treat analysis that consists of comparing probability of mortality between treatment groups at 7 years.	Non-inferiority analysis using clone-censor-weight strategy: 1. Each subject is cloned at study

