	
Kaplan-Meier to estimate probability of mortality in each arm
 
Construct a 95% confidence interval for the absolute difference between the two arms, <math>\Delta_{RD}</math>
 
Taking the type I error rate, alpha, to be 0.05, non-inferiority is concluded if the upper limit of a two-sided 90% = 100(1-2alpha)% confidence interval for <math>\Delta_{RD}</math> is less than the prespecified margin.
	
baseline; one clone assigned to each treatment strategy.
 
2. Person-time for each clones is censored when their observed treatment strategy is non-adherent. That is, clones assigned to undergo thyroid ultrasound within 3 months are censored at 3 months of follow-up if no ultrasound is performed. Similarly, clones assigned to not undergo an ultrasound within 3 months are censored at the time an ultrasound is performed.
 
3. A pooled logistic regression model is fit for the (conditional) probability of adherence, adjusting for a priori specified baseline factors that predict adherence.
 
4. A marginal structural pooled logistic regression model is fit to the mortality outcome data, as a function of time and treatment (with interaction), using inverse-probability of censoring weights from step 3.
 
5. Treatment-specific marginal probabilities of all-cause mortality are estimated from the fit in step 4, from which the causal risk difference, <math>\Delta_{RD}</math>, is estimated along with a two-sided 90% = 100(1-2alpha)% confidence interval (constructed via the bootstrap).
 
6. Taking the type I error rate, alpha, to be 0.05, non-inferiority is concluded if the upper limit of a two-sided 90% = 100(1-2alpha)% confidence interval for <math>\Delta_{RD}</math> is less than the prespecified margin.

Secondary Outcomes	
Cumulative over 7-years from PET:
 
Number of thyroid cancers
 
Number of thyroid ultrasounds
	
Cumulative incidence rate over 7-years from PET or to the end of the study period

	Number of thyroid biopsies Number of thyroid surgeries	
Exploratory Analysis	Types of thyroid cancer diagnoses	Same

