### **Explanation**

Primary Outcome Binary: 1 = died within follow-up period; 0 = did not die within follow-up period

follow\_up\_in\_days

Primary Outcome Continuous: Number of days from imaging examination to death, 10-years, or end of study, whichever comes first

thyroid\_cancer\_dx\_post\_pet

Secondary Outcome Binary: 1 = ICD10 C73 diagnosis after PET exam; 0 = no ICD10 C73 diagnosis

post\_pet\_thyroid\_excision

Secondary Outcome Binary: 1 = CPT code 60100 for thyroid excision performed after PET exam

thyroid\_ultrasounds

Secondary Outcome Continuous: Number of thyroid ultrasound exams performed after PET exam

thyroid\_biopsies

Secondary Outcome Continuous: Number of thyroid biopsies performed after PET exam

thyroid\_cancer\_subtype

Exploratory Outcome: ICD10 C73 subcategory

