### **Explanation**

Inclusion Criteria: 1 = thyroid nodule reported in imaging examination report; 0 = thyroid nodule not reported

age

Inclusion Criteria and Demographic: age in years at time of imaging examination

priorthyroidus

Exclusion Criteria: 1 = thyroid ultrasound performed within 3-years prior to imaging examination; 0 = thyroid US not performed within 3-years prior to imaging examination

priorthyroidcancer

Exclusion Criteria: ICD-10 C73 or ICD-9 193 before PET

NoSustainedCare

Exclusion Criteria: 1 = no provider note within system for 2-years following recommendation

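### Loss to follow-up for the secondary outcomes is checked only in the first 2 years, so patients who leave the health system later are counted as event-free, and absolute rates of work-up and thyroid cancer are understated

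*Combined protocol and SAP*

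**What the plan says.** Section 6.3 separates the two kinds of outcome. Mortality comes from death registries whether or not the patient stays in the system. For the secondary outcomes, "we will consider patients who did not have any provider note for 2-years following the PET-CT to be lost to follow-up". The matching variable in Section 7, NoSustainedCare, is one binary flag: "Exclusion Criteria: 1 = no provider note within system for 2-years following recommendation". No date of last contact is listed.

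The horizon is longer than the window checked. The secondary-outcome row of the Section 1.2 table asks for "Cumulative incidence rate over 7-years from PET or to the end of the study period". In the same table follow-up ends at "Earliest of death, 7-years from follow-up start, or study end", and the censoring row for the emulation reads "Administrative censoring Artificial censoring of clones". The only follow-up-time variable in Section 7 is "Number of days from imaging examination to death, 10-years, or end of study, whichever comes first".

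The non-mortality variables come from the health system's data warehouse. An absent record counts as no event: "Secondary Outcome Binary: 1 = ICD10 C73 diagnosis after PET exam; 0 = no ICD10 C73 diagnosis". Ultrasounds and biopsies are counts of recorded procedures. Section 8.4.4 reuses the weights built for following the ultrasound strategy and names no weight for staying in the system.

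**The concern.** Any single note in the first 2 years passes the rule. A patient with a note on day 10 and none afterwards passes, as does one who moves care in year 3. Both are then carried to the end of the horizon, and whatever happens to them elsewhere is recorded as nothing. Unobserved time is treated as observed, event-free time.

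These outcomes matter beyond their own hypotheses. Section 3 uses them to judge whether a non-inferior mortality result is clinically worthwhile. Section 4.1 allows the margin to be reconsidered in the light of the secondary benefits. If the burden of work-up is misstated, that judgement rests on poor evidence even when the mortality estimate is sound.

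**Working it through.** The plan gives no departure rate, no secondary event rate and no figure on this point to reproduce. What follows is an illustration, and its assumptions are marked.

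**How long the horizon is.** Section 4.3 gives a cut-off of 15 October 2025, for mortality; I assume the same for the secondary data. Seven full years are available for PETs up to about 15 October 2018. The latest PETs (31 December 2021) have 1,384 days, or 1,384/365.25 = 3.8 years.

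**Share of person-time unobserved.** Inputs:
- Death hazard μ = −ln(1 − 0.395)/10 = 0.0503 a year. This takes the 39.5% 10-year mortality of Section 8.2, which is from a CT/MRI sample, as exponential.
- Departure rate L = 0.05, 0.10 or 0.20 a year (assumed). Each patient is assumed to have a note before leaving, so the flag catches none of them. Where it does catch some, the shares below are somewhat high.

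With I(a, T) = (1 − e^(−aT))/a, person-time to death or T is I(μ, T), and the part that can be observed is I(μ + L, T).

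| L per year | I(μ+L, 7) / I(μ, 7) | Unobserved, 7 years | Unobserved, 3.8 years |
|---|---|---|---|
| 0.05 | 5.030 / 5.901 | 15% | 9% |
| 0.10 | 4.331 / 5.901 | 27% | 16% |
| 0.20 | 3.303 / 5.901 | 44% | 29% |

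With constant event hazards, absolute rates are understated by the same shares. For assumed true rates of 10 (no ultrasound) and 20 (ultrasound) per 1,000 person-years, the planned rule gives 8.5 and 17.0, then 7.3 and 14.7, then 5.6 and 11.2.

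**Effect on the between-arm contrast over 7 years.** The rate ratio is ultrasound over no ultrasound. The difference is in mean events per patient. All event and departure rates are assumed.

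| Scenario | Ratio: true → planned rule | Difference: true → planned rule |
|---|---|---|
| Constant hazards 0.02 vs 0.01, equal departure 0.05 / 0.10 / 0.20 | 2.00 → 2.00 in all three | 0.059 → 0.050 / 0.043 / 0.033 |
| Same hazards, no-ultrasound arm leaves faster (0.15 vs 0.05) | 2.00 → 2.67 | 0.059 → 0.063 |
| Same hazards, ultrasound arm leaves faster (0.15 vs 0.05) | 2.00 → 1.50 | 0.059 → 0.025 |
| Ultrasound-arm events early (0.10 in year 1, then 0.0067) vs constant 0.01, equal departure 0.05 / 0.10 / 0.20 | 2.21 → 2.43 / 2.67 / 3.17 | 0.072 → 0.072 / 0.072 / 0.072 |
| No-ultrasound events early (0.03 in year 1, then 0.0065) vs constant 0.02, equal departure 0.10 | 1.93 → 1.73 | 0.057 → 0.037 |

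The undercount appears in every scenario. The direction of the bias in the ratio does not stay fixed.

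**Does censored person-time alone cure it?** With constant hazards it does: events divided by I(μ + L, 7) return 10 and 20 per 1,000. In the early-event scenario it does not. Departure is equal, so both denominators shrink by the same factor and the crude ratio stays at 2.43 / 2.67 / 3.17 against a true 2.21. A time-specific estimate is needed.

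**The case against.** The wording in Section 6.3 could be stretched to mean any later 2-year gap in notes. The single undated flag in Section 7 makes that strained, and neither the follow-up definition nor the time variable would act on such a gap.

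A reader might infer that the rule inflates the rate ratios, in the direction of the secondary hypotheses in Section 8.1. The argument would be that patients scanned in the system tend to stay in it. The documents do not support that as a conclusion. They give no attrition by arm, and equal or reversed departure leaves the ratio unchanged or lowers it. Inflation is plausible if work-up soon after the scan brings ultrasound-arm events forward, but that is a supposition about timing. Section 8.4.4 also names risk differences or odds ratios, and a risk difference can shrink, which works against the hypotheses.

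The plan has partial protection. Eligibility requires an in-system note in the prior 36 months. The adjustment covers ordering department, care level, PET type (with a category for outside PETs), comorbidity and disease status. This may narrow a difference in retention between arms. It does not detect departure, and it does nothing for the absolute undercount.

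Only secondary outcomes are involved. That stands, and it limits how serious the point is.

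**Conclusion.** The point holds for the absolute rates. Followed as written, the plan counts time after departure as event-free, for up to 7 years for PETs through about October 2018 and for at most 3.8 years for the latest. The undercount over 7 years is about 15%, 27% and 44% at departure rates of 0.05, 0.10 and 0.20 a year. This rests on assumed exponential departure, constant event hazards and a death hazard borrowed from the CT/MRI sample. It is smaller for shorter follow-up.

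For the contrasts, the supportable statement is that they may be biased in either direction. A reader might also infer that the non-inferiority conclusion is compromised. It is not, since Section 6.3 makes ascertainment of death independent of continued care in the system. What suffers is the evidence on work-up burden used to interpret that conclusion. The change should be made before analysis.

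**What to change.** In Sections 1.2 (follow-up end, censoring and secondary-outcome rows), 6.3 and 8.4.4, for the secondary outcomes only:

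1. Derive an in-system follow-up end date from note timestamps, applying the 2-year no-note criterion on a rolling basis: the start of the first 2-year gap. State a rule for gaps the data cut-off leaves incomplete; with an October 2025 cut-off, a gap that starts after October 2023 cannot be confirmed.
2. Censor at the earliest of that date, death, 7 years or study end, with death handled as a competing event.
3. Multiply the adherence weights by inverse-probability-of-retention weights. Consider time-varying predictors of departure, since the current weight model uses baseline factors only.
4. Estimate time-specific cumulative incidence for cancer and surgery, and the mean cumulative count for ultrasounds and biopsies. This needs event dates, which the Section 7 variable list does not show.
5. Report in-system follow-up by arm.
6. Keep the analysis under the current rule as a sensitivity analysis.

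In the same edit, reconcile Section 6.3 (lost to follow-up, secondary outcomes only) with Section 7, which labels the flag an exclusion that Section 5.2 does not list. Also reconcile the rate ratios of Section 8.1 with the measures named in Section 8.4.4.

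The cost is one derived date from timestamps the existing rule already needs, event dates from the same warehouse, one extra weight model and some wording. There will be less person-time and wider intervals, and a patient with a genuine 2-year gap in care is censored early. Some dependence may remain because work-up itself generates notes, which is a further reason for the sensitivity analysis.

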## 7 STUDY PROCEDURES

All of the following variables, except the last 12 disease status variables, will be extracted from the electronic health system research data warehouse using Snowflake, SQL scripts, and Python scripts. The extracted data will be coded as described in R. The last 12 disease status variables will be extracted and coded from the PET-CT reports by an instance of ChatGPT4 in Azure that is secure behind the healthcare system firewall. Data will be included for patients who had PET-CT examinations performed between 1/1/2015 and 12/31/2021, which allows a 3-year period for propagation of death records to our healthcare system's electronic health records. All HIPAA rules and local institutional and IRB requirements will be followed for data collection.

### **Exposure Variable**

thyroidus3mospost

### **Explanation**

Exposure: 1 = thyroid ultrasound performed within 3-months following imaging examination; 0 = thyroid US not performed within 3-months following imaging examination

### **Outcome Variables**

mortality\_binary

### **Explanation**

Primary Outcome Binary: 1 = died within follow-up period; 0 = did not die within follow-up period

follow\_up\_in\_days

Primary Outcome Continuous: Number of days from imaging examination to death, 10-years, or end of study, whichever comes first

thyroid\_cancer\_dx\_post\_pet

Secondary Outcome Binary: 1 = ICD10 C73 diagnosis after PET exam; 0 = no ICD10 C73 diagnosis

post\_pet\_thyroid\_excision

Secondary Outcome Binary: 1 = CPT code 60100 for thyroid excision performed after PET exam

thyroid\_ultrasounds

Secondary Outcome Continuous: Number of thyroid ultrasound exams performed after PET exam

thyroid\_biopsies

Secondary Outcome Continuous: Number of thyroid biopsies performed after PET exam

thyroid\_cancer\_subtype

Exploratory Outcome: ICD10 C73 subcategory

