## 5 STUDY POPULATION

### 5.1 INCLUSION CRITERIA

In order to be included in this study, an individual must meet all of the following criteria:

1. Age  $\geq 18$
2. Thyroid nodule on PET-CT performed 1/1/2015 to 12/31/2021
3. At least one clinical note in the EHR from the 36-month window prior to the PET

Note, there are no restrictions on the indication for the index PET-CT.

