#### **Additional Patient Variables**

#### **Explanation**

sex	Demographic: 1 = male; 2 = female; 3 = other/unknown
adi	Demographic: national area deprivation index on scale 0 (low deprivation) to 100 (high deprivation) based on listed home address in 2025
language	Demographic: self-reported language
race	Demographic: self-reported race
ethnicity	Demographic: self-reported ethnicity
smoking	Potential Confounder: 0 = never; 1 = former; 2 = active; No_self-report = not reported; most recently recorded prior to imaging
alcohol	Potential Confounder: 0 = never; 1 = occasional; 2 = heavy; most recently recorded prior to imaging
obesity	Potential Confounder: 1 = diagnosis of obesity (ICD-10 E66, ICD-9 278.00 or 278.01) at time of imaging examination OR OR cacluated BMI >30 at timepoint within 1 year before and closest to imaging examination; 0 = no diagnosis of obesity or BMI >30
metabolic_syndrome	Potential Confounder: 1 = diagnosis of metabolic syndrome (ICD-10 , ICD-9 277.7) at time of imaging examination; 0 = no diagnosis of metabolic syndrome at time of imaging examination
mi	Mortality Risk Adjustor: Myocardial Infarction: ICD-10 I21.9; ICD-9 410; recorded prior to date of imaging examination
chf	Mortality Risk Adjustor: Congestive Heart Failure: ICD-10 I50; ICD-9 428; recorded prior to date of imaging examination
pvd	Mortality Risk Adjustor: Peripheral Vascular Disease: ICD-10 I70, I73; ICD-9 443, 440.2, 440.3, 440.4; recorded prior to date of imaging examination

cva	Mortality Risk Adjustor: Cerebrovascular Accident: ICD-10 I60-I63, G45; ICD-9 430-438; recorded prior to date of imaging examination
dementia	Mortality Risk Adjustor: Dementia: ICD-10 F01-F03; ICD-9 290; recorded prior to date of imaging examination
cpd	Mortality Risk Adjustor: Chronic Pulmonary Disease: ICD-10 J42-J44; ICD-9 491-492; recorded prior to date of imaging examination
ctd	Mortality Risk Adjustor: Connective Tissue Disease: ICD-10 M30-M36; ICD-9 710; recorded prior to date of imaging examination
pu	Mortality Risk Adjustor: Peptic Ulcer Disease: ICD-10 K25-K28; ICD-9 531-534; recorded prior to date of imaging examination
ld	Mortality Risk Adjustor: Liver Disease: ICD-10 K70-K77; ICD-9 570-573; recorded prior to date of imaging examination
dm	Mortality Risk Adjustor: Diabetes Mellitus: ICD-10 E8-E13; ICD-9 249-250; recorded prior to date of imaging examination
hemiplegia	Mortality Risk Adjustor: Hemiplegia: ICD-10 G81; ICD-9 342; recorded prior to date of imaging examination

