ckd	Mortality Risk Adjustor: Chronic Kidney Disease: ICD-10 N18; ICD-9 585; recorded prior to date of imaging examination
cancer	Mortality Risk Adjustor: Cancer: ICD-10 C00-C96; ICD-9 140-209; recorded prior to date of imaging examination
obesity_icd	Mortality Risk Adjustor: Diagnosis of obesity (ICD-10 E66, ICD-9 278.00 or 278.01) at time of imaging examination
bmi	Mortality Risk Adjustor: Body mass index at time of imaging examination
hncancer_binary	Mortality Risk Adjustor: Head/Neck Cancer: ICD-10 C00-C14; ICD-9 140-149; recorded prior to date of imaging examination
radiation_binary	Mortality Risk Adjustor: Radiation Therapy: CPT 77401-77416, G6003-G6014, 77385-77386, G6015-G6016
priorneckradiation	Mortality Risk Adjustor: Prior head/neck cancer radiation therapy (ICD-10 C00-C14 or ICD-9 140-149 and CPT 77401-77416, G6003-G6014, 77385-77386, or G6015-G6016 both recorded prior to date of imaging examination, then priorneck radiation =1; otherwise, 0)
Fiveyr_atPET	Mortality Risk Adjustor: 5 year survival probability associated with cancer dx received before PET exam (if multiple cancers before PET, lowest survival probability)
NeckNodes	Potential Confounder: 1= PET-CT report indicates that there are neck or supraclavicular lymph node metastases
AxillaryNodes	Potential Confounder: 1= PET-CT report indicates that there are axillary lymph node metastases
MediastinalNodes	Potential Confounder: 1= PET-CT report indicates that there are mediastinal (including paratracheal, paraesophageal, prevascular, subcarinal, perihilar, or hilar) lymph node metastases
AbdominalNodes	Potential Confounder: 1= PET-CT report indicates that there are abdominal (including peri-portal, celiac, mesenteric, retroperitoneal, iliac) lymph node metastases
InguinalNodes	Potential Confounder: 1= PET-CT report indicates that there are inguinal lymph node metastases

Brain	Potential Confounder: 1= PET-CT report indicate that there is likely primary malignancy or metastases in the lungs
Face	Potential Confounder: 1= PET-CT report indicate that there is likely primary malignancy or metastases in the face (e.g. pharynx, salivary glands, etc)
Lung	Potential Confounder: 1= PET-CT report indicate that there is likely primary malignancy or metastases in the lungs
Pleura	Potential Confounder: 1= PET-CT report indicate that there is likely primary malignancy or metastases in the pleura

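### The post-PET thyroid-cancer outcome counts only ICD-10 C73, while prior thyroid cancer is found by C73 or ICD-9 193, so a post-PET case coded only as 193 would be recorded as no cancer

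*Combined protocol and SAP*

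**What the plan says.** All references are to the combined protocol and SAP.

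- **Outcome after the PET.** Section 7, Outcome Variables, defines thyroid_cancer_dx_post_pet as "Secondary Outcome Binary: 1 = ICD10 C73 diagnosis after PET exam; 0 = no ICD10 C73 diagnosis". The exploratory variable thyroid_cancer_subtype is also built on C73 alone.
- **Same disease before the PET.** Section 7, Inclusion/Exclusion Variables, defines priorthyroidcancer as "Exclusion Criteria: ICD-10 C73 or ICD-9 193 before PET".
- **Accrual.** Section 5.1 admits "Thyroid nodule on PET-CT performed 1/1/2015 to 12/31/2021".
- **Outcome window.** The emulation column of Section 1.2 gives the secondary outcomes as "Cumulative incidence rate over 7-years from PET or to the end of the study period", so counting starts at the PET.
- **Exposure.** Under Section 6.1, "exposure is whether a thyroid ultrasound is performed within 3 months of the index PET-CT".
- **Other ICD-9 use.** Most diagnosis covariates in Section 7 list both code systems but look back before the PET, for example "Cancer: ICD-10 C00-C96; ICD-9 140-209; recorded prior to date of imaging examination". Three are tied to the imaging date instead: obesity ("1 = diagnosis of obesity (ICD-10 E66, ICD-9 278.00 or 278.01) at time of imaging examination"), metabolic_syndrome ("1 = diagnosis of metabolic syndrome (ICD-10 , ICD-9 277.7) at time of imaging examination") and obesity_icd.

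**The concern.** The plan has two code lists for one disease, and the shorter one defines the outcome. If any clinic or hospital in the system was still entering ICD-9 codes after the first index PETs, the outcome query cannot see thyroid cancers recorded in that period.

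The affected period lies at the start of follow-up for the earliest PETs. A three-month ultrasound would be expected to bring cancers to light early, whereas cancers that surface later without ultrasound would mostly fall in covered time. A loss could therefore be uneven between the arms and pull the thyroid-cancer ratio toward 1, against the secondary hypothesis in Section 8.1.

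The count matters for interpretation. Section 3 uses the secondary outcomes to judge whether a non-inferiority result is clinically meaningful, and Section 4.1 allows the margin to be reconsidered in their light. The adjustment set in Section 4.1 does not include exam_year, which carries none of the adjustment labels in Section 7. Adjusting for era could not restore a case already coded 0 in any event.

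**Working it through.** The plan states no figure on this point, so there is none to reproduce. The check has two parts.

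**1. Code sets side by side**

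| Use | ICD-10 | ICD-9 |
|---|---|---|
| Prior thyroid cancer (exclusion) | C73 | 193 |
| Thyroid cancer after PET (secondary outcome) | C73 | none |
| Thyroid cancer subtype (exploratory) | C73 | none |

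By the wording of the outcome, a patient with 193 and no C73 after the PET receives 0.

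**2. How much follow-up could be uncovered**

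Inputs:
- Accrual from 1 January 2015 to 31 December 2021 (Section 5.1): 7 × 365 + 2 leap days = 2,557 days.
- Uniform accrual (assumption).
- Changeover date *c* from ICD-9 to ICD-10 (assumption, varied because the documents give none). Let *w* be the days from 1 January 2015 to *c*.

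Formulas:
- Share of PETs with any uncovered follow-up = *w* / 2,557.
- Share of diagnoses made at lag *L* days that fall before *c* = max(0, *w* − *L*) / 2,557.
- Uncovered share of seven-year person-time, with no deaths or truncation = (*w*² / 2) / (2,557 × 2,557), since seven years is also 2,557 days.

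| Assumed changeover | *w* | PETs with a gap | Diagnosed at 30 days | At 91 days | At 182 days | Person-time |
|---|---|---|---|---|---|---|
| 1 Jan 2015 | 0 | 0% | 0% | 0% | 0% | 0% |
| 1 Apr 2015 | 90 | 3.5% | 2.3% | 0% | 0% | 0.06% |
| 1 Jul 2015 | 181 | 7.1% | 5.9% | 3.5% | 0% | 0.25% |
| 1 Oct 2015 | 273 | 10.7% | 9.5% | 7.1% | 3.6% | 0.57% |
| 1 Jan 2016 | 365 | 14.3% | 13.1% | 10.7% | 7.2% | 1.02% |

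Example for 1 October 2015: 273 / 2,557 = 10.7%; (273 − 91) / 2,557 = 7.1%; (273 − 182) / 2,557 = 3.6%. Among the affected PETs the mean gap is 273 / 2 = 136.5 days.

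**From calendar time to lost cases.** The table bounds the diagnoses whose *first* code would be ICD-9. A case is lost only if no C73 code ever follows. The documents do not say how often that happens. If 10% to 30% were never recoded (assumption), then with a 1 October 2015 changeover the loss is 7.1% × 0.10 to 7.1% × 0.30 = 0.7% to 2.1% of cancers diagnosed at three months, and 3.6% × 0.10 to 3.6% × 0.30 = 0.4% to 1.1% at six months.

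**Ceiling on the ratio.** Suppose every ultrasound-arm cancer is diagnosed at three months, none is lost in the other arm, and none is recovered. The ratio is then multiplied by 1 − 0.071 = 0.929 (1 October 2015) or 1 − 0.107 = 0.893 (1 January 2016). With 10% to 30% never recoded and the October date, the multiplier is 0.993 to 0.979.

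**After the fix.** With 193 added, the uncovered window is 0 days for every PET, whatever the changeover date.

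**The case against.** **ICD-9 use after the PET is inferred, not stated.** This stands. Nearly all the ICD-9 lists look back, and they show only that ICD-9 occurs in patients' histories. The imaging-date wording for obesity and metabolic syndrome points further, but it can also mean a condition present at imaging and coded earlier. A reader might infer that the plan itself establishes ICD-9 coding during follow-up. The documents suggest this but do not prove it.

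**Most early cases should be recovered.** This largely stands. The outcome is satisfied by any C73 code after the PET, within a window of up to seven years. Section 2.2 gives 98.6% five-year survival for thyroid cancer. Against that, the same section expects 30% to 50% ten-year mortality in PET patients, so some would die before recoding. Section 6.3 treats patients with no provider note for two years after the PET as lost for the secondary outcomes, which removes some, but not all, of those who leave care.

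**A late first-code date does little harm.** This partly stands. Section 7 lists no thyroid-cancer diagnosis date, the outcome is binary, and Section 8.4.4 reports risk differences or odds ratios. Delay would matter only if timing is analysed, as the rate language in Sections 1.2, 3 and 8.1 leaves possible.

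**The bias could not create a false finding of excess diagnosis.** If the loss falls mainly on the ultrasound arm, this is correct: it runs toward 1. It could still understate the overdiagnosis that the secondary outcomes are meant to show.

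**Conclusion.** The inconsistency is real and should be corrected, but its effect is probably small. As written, a post-PET thyroid cancer recorded only as ICD-9 193 is coded as no cancer, and no mapping between code systems is described.

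For assumed changeover dates from 1 January 2015 to 1 January 2016, 0% to 14.3% of PETs have some uncovered follow-up, and at most 0% to 10.7% of diagnoses made at three months would first carry only an ICD-9 code. These figures rest on uniform accrual and an assumed date, and later C73 codes reduce the actual loss.

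Two stronger conclusions are tempting and unsupported. One is that a large part of the early outcome window is lost. On the October date, 2015 PETs taken alone have about 63% of their first 90 days uncovered. That is calendar time in one accrual year, not a share of cancers missed; over the whole cohort and full follow-up, uncovered person-time is about 0.6%. The other is that the loss is necessarily differential. That is plausible given the three-month exposure, but the documents give no timing of cancer diagnoses in either arm, so neither the imbalance nor its size is shown.

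The primary mortality outcome does not use these codes and is unaffected.

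**What to change.** Define thyroid_cancer_dx_post_pet as the first ICD-10 C73 or ICD-9 193 code after the PET, matching priorthyroidcancer, and use the earlier of the two dates wherever timing is analysed. Have thyroid_cancer_subtype classify cases found only through 193 explicitly, for example as subtype unknown, so that the subtype table adds up to the outcome count. If the data warehouse already maps ICD-9 entries to ICD-10, saying so in Section 7 would answer the point.

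The cost is one more code in the outcome query, already in use for the exclusion, and one more subtype category. No model or sample-size change follows.
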